7.0 Data Monitoring Plan

Participants will be randomized to one of the four arms: metformin, placebo, and metformin / placebo and lifestyle intervention using the Department of Biostatistics Clinical Trial Conduct Website (CTC website). Participants who do not meet these criteria will be considered nonevaluable, removed from study and will not be counted toward the actual accrual goal. We plan to accrue 100 evaluable participants.

We will use a form of adaptive randomization called minimization, which is similar to stratification in that participant characteristics are used to assign them to the treatment conditions [75, 76]. Minimization results in better group balance with respect to participant characteristics. In minimization, before a participant is assigned to a treatment group, the total numbers of participants in each group with similar covariate characteristics are totaled. The totals are based on the marginal sums of the covariates so that each covariate is considered separately. The treatment assignment of a participant is determined based on which group would provide the best overall balance with respect to those covariates. Covariates that will be used in randomization of participants in this study are BMI, age, and whether the participant meets current guidelines for exercise recommended by the Physical Activity Guidelines for Americans. These guidelines recommend that adults engage in moderate physical activity at least 150 minutes per week or in vigorous activity 75 minutes per week [77]. The baseline level of activity for each participant will be measured when they complete the Godin questionnaire, which is part of their survey packet, which will be completed before their Screening Visit 2 appointment. The Research Dietitian/Research Coordinator will determine if the participant is currently meeting these recommendations and provide

this data to the Research Nurse for randomization.

Randomization will be performed by the research nurse using the website created by the Department of Biostatistics. The research nurse will then inform the pharmacist of randomization group (A, B, C, or D) for study drug administration. The Research Dietitian/Research Coordinator who is in charge of administering the lifestyle intervention will be given access to the randomization website and informed of lifestyle intervention randomization code to determine whether the participant has been randomized to the lifestyle intervention.

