- a) randomized to one of the four intervention groups using the Department of Biostatistics Clinical Trial Conduct Website. See section 7.0 for details.
- b) given prescription to fill the study medication at the pharmacy at MD Anderson Cancer Center.
- c) participant will be provided education on recording and monitoring daily intake of study medication into the Pill Diary. See Appendix M for Pill Diary.

- d) review and report side effects of the study medication.

Once the participant is randomized, the research nurse will notify the pharmacist to inform them of the randomization code in order to keep study staff blinded to assignment to metformin vs. placebo.

In-person toxicity assessments will be performed at the end of the first, second, third, and fourth month (plus or minus 10 days). Phone assessments will be done periodically as needed to assess for adverse effects. At the end of the fourth month of the study, the participant will return for the **Post-Treatment Evaluation** to repeat all measurements (all blood tests, anthropometric assessments, second biopsy, and survey packet) taken at the Screening Visits (1& 2). The participant will also be given a Satisfaction Questionnaire, based on their intervention, in advance to complete and return at this visit.

One year after baseline (+/- 1 month), participants will be contacted to complete a 1 Year Follow-Up Evaluation. This evaluation will include anthropometrics assessments, including a DEXA scan, the survey packet, and blood tests collected from the 4th month visit (see Table 5: Study Parameters for the list of laboratory test to be collected for 1 year Follow-up Evaluation). During this visit, the participant will also be compensated with a parking voucher to cover the cost of parking during the visit.

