6.4 Toxicity assessment

The summary of toxicity assessment for in-person and phone is listed below.

A. In-person assessment include:

- physical exam (only on 1st month)
- weight
- review of study medication side effects (as listed in consent and instruct participant to call if they experience symptoms of abdominal pain, anorexia, nausea, jaundice, and change in urine color)
- ALT and creatinine levels.
- Dispense Pill Diary and prescription.

B. Phone assessment include reported symptoms of:

- gastrointestinal (abdominal pain and severe diarrhea)
- liver (jaundice) and review ALT lab results
- kidney (changes in urine color and amount) and review creatinine lab results
- heart (CHF)
- rare side effects listed in consent

The in-person toxicity assessment will be at the end of each month and will be a month from Randomization / Visit 3. All participants must agree to keep a drug administration diary (Pill Diary). This diary will be signed by both the participant and research nurse and reviewed during each clinic visit to verify compliance. The medication administration record will be filed in the participant's chart. Any discrepancies will be noted along with

the reason, if known. Any remaining pills will also be returned at each clinic visit and documented.

Participants with mild elevations in ALT (3x ULN), will continue study drug at same dose, and have another ALT drawn 30 days later. If ALT levels are \geq 4x ULN, the study drug will be stopped, and participant removed from the study. Participants with an elevation in creatinine of \geq 2.5x ULN will be taken off of the drug and removed from the study. The study drug will be stopped and participant removed from study if the participant reports symptoms of congestive heart failure (CHF) such as: fatigue, tightness or congestion in the chest, edema to ankles or lower extremities, and shortness of breath.

Telephone contacts will be made periodically as needed to assess on the first, second, third, and fourth month (plus or minus 10 days) to encourage compliance and assess for the presence of toxic or adverse effects. Participants experiencing toxic or adverse effects will be referred to MD Anderson health providers for medical care however medical care will be billed to the participant or participant's insurance provider. All participants will be contacted by telephone 4 weeks after completion of the study for follow-up and toxicity assessment.

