9.0 Statistical Considerations

This is a partially blinded, randomized study to evaluate the effects of intervention upon Ki-67 and other biomarkers. Participants and researchers will be blinded with regard to assignment of study drug (placebo vs. metformin) but they will not be blinded with regard to assignment of lifestyle intervention. We will use a form of adaptive randomization called minimization, which is similar to stratification in that participant characteristics are used to assign them to the treatment conditions to achieve better group balance. Groups will be balanced with regard to age (50-65 years), BMI (Class I and II: 30.0-39.9 and Class III or greater: ≥ 40), and whether they meet current exercise guidelines as recommended by the Physical Activity Guidelines for Americans.

The primary objective of this study is to evaluate the effect of intervention (metformin and/or lifestyle intervention) on Ki-67. Secondary endpoints include examination of intervention on:

- (a) genes relevant to estrogen dependent endometrial proliferation, hyperplasia and cancer using Q-PCR (PCNA, sFRP4, RALDH2, IGF-1R, survivin, and EIG121),
- (b) biomarkers specific to the effect of metformin treatment (phospho-AMPKa, phospho-ACC, phospho-mTOR and phospho-S6 ribosomal protein).

Additionally, we will examine changes in serum levels of estradiol, estrone, testosterone, DHEA-S, sex hormone binding globulin (SHBG), adiponectin, glucose,

HbA1c, insulin and insulin-like growth factor-1 (IGF-1) and all biobehavioral outcomes, such as changes in body composition, physical activity, quality of life (QoL), diet, etc.

We will analyze differences in Ki-67 and other outcomes using 2x2 ANOVA models. If lifestyle intervention is found to affect change in Ki-67 expression or other outcomes, we will use the methods described by Baron and Kenney [78] to determine whether these changes were mediated by weight loss, body composition changes, physical activity changes, and dietary changes. Differences between arms with regard to adverse events and other toxicities will be examined using Fisher's exact tests. Changes from baseline lab values will be examined 2x2 ANOVA models.

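### The research nurse, who is meant to be blinded to drug, relays what appears to be a fixed arm letter (A to D), so decoding one letter would reveal metformin or placebo for about 50 women.

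*Combined protocol and SAP*

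**What the plan says.** Section 7.0 (Data Monitoring Plan) states: "Randomization will be performed by the research nurse using the website created by the Department of Biostatistics". The nurse is then to "inform the pharmacist of randomization group (A, B, C, or D") so that study drug can be dispensed. Section 5.4 (Randomization / Visit 3) gives the reason for the relay: it is done "in order to keep study staff blinded to assignment to metformin vs. placebo".

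Section 9.0 sets out who is blinded to what: "Participants and researchers will be blinded with regard to assignment of study drug (placebo vs. metformin) but they will not be blinded with regard to" the lifestyle assignment. Section 6.1 says the same of the investigator and participants. Section 5.4 also schedules the first lifestyle session for the day of randomization.

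Section 6.4 (Toxicity assessment) says of the pill diary: "This diary will be signed by both the participant and research nurse and reviewed during each clinic visit to verify compliance". Section 3.7 lists diarrhea, nausea/vomiting, flatulence and abdominal discomfort among the side effects, without rates. Section 5.4 puts 25 women in each of the four arms.

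The plan does not describe participant-specific drug numbers. It has no rule that keeps the letter from staff who see participants during follow-up.

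**The concern.** The person who carries the code belongs to the staff whom the code is meant to blind. A code shared by a whole arm protects the blind less well than one unique to each woman. With individual numbers, a revealing symptom tells staff something about one participant. With a shared letter, every participant's experience adds evidence about the same unknown, and one correct inference applies to everyone under that letter.

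The open lifestyle factor makes the decoding easier. Staff who know a woman's letter and whether she attends lifestyle sessions can sort the four letters into two pairs. Within each pair, one letter is metformin and the other is placebo.

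At stake are the judgements that drug blinding supports: attribution of adverse events (section 10.6), the view taken of compliance, and removal at the investigator's discretion (section 8.2). Section 9.0 counts women who discontinue early as having no change from baseline, so a removal influenced by a guessed assignment could reach the primary comparison.

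**Working it through.** The plan states no figure on this point, so there is none to reproduce. The check has two parts.

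**1. How many women one letter reveals**

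- Four arms of 25 (section 5.4): 4 × 25 = 100.
- Each lifestyle stratum holds two letters, one metformin and one placebo. Identifying one identifies the other: 2 × 25 = 50 women.
- This needs each letter to stand for one arm throughout. Four letters for four arms make that the natural reading, but the plan does not say so.

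**2. How readily the letters could be told apart**

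The documents give no gastrointestinal event rates, so the rates below are assumptions. Let pM be the rate on metformin, pP the rate on placebo, and n the number of women seen under each letter.

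- Guessing one woman from her own symptoms (metformin if she has an event): accuracy = 0.5 × pM + 0.5 × (1 − pP).
- Guessing between the two letters (metformin is the letter with more events, ties split evenly): accuracy = P(XM > XP) + 0.5 × P(XM = XP), with XM and XP independent binomial counts on n women each.

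Worked case, 30% v 10%:

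- One woman: 0.5 × 0.30 + 0.5 × 0.90 = 0.60.
- n = 10: 0.8098 + 0.5 × 0.1197 = 0.870.
- n = 25: 0.9513 + 0.5 × 0.0274 = 0.965.

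| Assumed rates, metformin v placebo | One woman | Letters, n = 10 | Letters, n = 25 |
|---|---|---|---|
| 30% v 10% | 60% | 87% | 96.5% |
| 20% v 10% | 55% | 73% | 84% |
| 30% v 20% | 55% | 69% | 79% |
| 20% v 20% | 50% | 50% | 50% |

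Pooling by letter is more informative than guessing woman by woman whenever the rates differ. It gives nothing when they are equal.

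**A stricter measure.** Forced-guess accuracy is not the chance that staff notice a clear pattern. The table below gives the probability that the difference between letters is in the right direction and reaches two-sided Fisher p < 0.05.

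| Assumed rates | n = 10 | n = 25 |
|---|---|---|
| 30% v 10% | 6% | 30% |
| 20% v 10% | 1% | 9% |

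**The case against.** The strongest case on the other side is that the documents show less than a reader might infer.

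- **The nurse as toxicity assessor.** This is tempting because the diary sentence stands in the toxicity section, but no section says it. Section 6.4 has the nurse sign a diary reviewed to verify compliance. Section 3.8 refers to symptoms reviewed with research staff. Sections 10.3 and 10.6 have the investigator document adverse events and judge relatedness. Whether the investigator sees the letter is not stated. This objection stands, so the point rests on the nurse's stated roles only.
- **The dietitian or coordinator.** Section 7.0 gives this person access to the website, but says that what is communicated is the lifestyle code. Nothing shows that the drug letter is displayed. This stands.
- **Emergency unblinding.** The documents describe no procedure for it, so a whole arm being opened by one such event is hypothetical. It is not relied on here.
- **The size.** The rates are assumed, and a guess is not a visible excess. The figures at 25 per letter need full enrolment with outcomes seen, when few compliance or removal decisions remain. This stands as a limit. The figures at 10 per letter bear more on decisions made during the trial.
- **The route to Ki-67.** The slides are stained and read in the histology and pathology cores (sections 2.6, 11.1 and 12.6). Section 8.5 defines non-compliance numerically, and section 6.4 ties some removals to laboratory thresholds. This stands: several steps separate a decoded letter from a biased primary result.

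These objections do not remove the procedural conflict. Section 7.0 gives a shared code to someone whom section 5.4 means to keep blinded, and nothing described prevents information from accumulating by letter.

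**Conclusion.** The point holds as a foreseeable weakness in the blinding procedure. The nurse handles what appears to be a fixed arm code and also takes part in follow-up, and the open lifestyle factor reduces the unknown to one choice between two letters in each stratum. Decoding one letter would expose about 50 women.

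Under assumed rates of 20% v 10% to 30% v 10%, the two letters are guessed correctly 73% to 87% of the time after 10 women each and 84% to 97% after 25, against 55% to 60% for single-woman guesses. These figures rest on a fixed letter for each arm, on the assumed rates, and on someone comparing symptoms by letter.

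A reader might infer that the blind will fail or that the Ki-67 result is compromised. The documents support neither. The possible effect on the primary endpoint runs only through compliance judgements and discretionary removals that then count as zero change, and its size cannot be derived from what is given. The change is worth making because it costs little and protects blinding that the plan already promises.

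**What to change.** - Have the randomization website send the drug assignment directly to the pharmacist, without passing through the research nurse.
- Show the nurse, the dietitian or coordinator and other follow-up staff only whether the participant is assigned to the lifestyle intervention.
- Label study drug with participant-specific numbers in place of four shared letters, with the link held only by pharmacy and the randomization system.
- State in sections 6.4 and 10.3 which role assesses toxicity, and confirm that this role has no access to the drug code.

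The cost is a change to website permissions, a change to labelling and slightly more pharmacy work. Sample size, visits and treatment are unaffected.

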7.1 Protocol compliance and assessment of toxicity data

The attending physician must see each participant prior to beginning study drug. All required interim and pretreatment data should be available to evaluate toxicities, assign grade, and make a determination regarding continuing treatment.

7.2 Data collection Plans

Protocol data will be entered into the following plans: Clinical Oncology Research System (CORe) / Protocol Data Management System (PDMS), Access Database, ASA server, MD Anderson Cancer Center (MDACC) Behavioral Science server, and excel spreadsheet after each course of therapy. A brief explanation for required but missing data should be recorded as a comment. See below for the list of the specific data stored in PDMS and CORe:

- PDMS
 - Monthly medication administration dates
 - Doses taken
 - Laboratory results
 - Clinic visits
 - Diagnostic test (EMB)
- CORe
 - Pre-registration
 - Adverse events entry

All behavioral and anthropometric data components, including height, weight, waist and hip circumference, exercise diary, and survey packet data will be collected and kept in an Access Database. The ASA24 data is stored on the ASA site's server until we request the data for analysis. The data is sent to us within 48 hours and then the file is stored on our server. The Accelerometer data will also be stored on our server at MDACC (Department of Behavioral Science) until the statistician retrieves the data for analysis. The DEXA scan data is downloaded into a file such as excel (Department of Behavioral Science) and then is stored on the server as well.

8.0 Criteria for Removal from the Study

- 8.1 Subjects are free to leave the study at any time.
- 8.2 Participants may be removed from the study at the discretion of the investigator if there is sufficient reason to suspect that the participant is not compliant with the study requirements.
- 8.3 If at any time during the study, the participant experiences symptoms of congestive heart failure or renal failure, drug will be stopped and the participant taken off study.
- 8.4 Abnormal baseline endometrial biopsy or the endometrial biopsy is unable to be performed.
- 8.5 Non-compliance: Non-compliance will be defined as a participant missing more than 4 consecutive doses per month or a total of more than 10 doses during the 4 month period.
- 8.6 Lost to follow-up: Diligent attempts must be made by telephone and letter to determine the circumstances for loss to follow-up, since loss may be related to study drug.

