5.3.1 Endometrial biopsy

An endometrial pipelle biopsy will be performed at the Screening Visit 2 and at the 4th month on days 115-125 (plus or minus 10 days) into treatment in all participants from (all four arms) both groups.

In addition to histologic examination, each endometrial biopsy will be examined for proliferation markers as well as other biomarkers. The second biopsy in the no treatment group is important in order to determine variability in the biomarkers due to sampling. In preliminary data from the Wyeth-Ayerst Study, we did see variability in certain transcript levels at the 3 and 6 month time points even in the placebo control group. Therefore, we feel strongly in this study that women in both groups undergo a 4 month EMB.

Risks of office endometrial biopsy are small, and while there are no published data on risk of perforation, we believe that the risk is less than 1/1000. Even in those participants in whom uterine perforation occurs, observation alone is usually sufficient. The severe perforations requiring laparotomy and emergent hysterectomy are not seen in office endometrial biopsies, rather in Dilatation and Curettage (D & C) procedures performed in the operating room.

Participants who have no allergies will be instructed to take orally Non- Steroidal Anti-inflammatory Drugs (NSAIDs) before and after the biopsies to reduce pain and cramping. The NSAIDs medications are available over the counter (See Section 5.2 for the recommended dose).

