6.1 Treatment

Prior to beginning therapy, participants will have a baseline endometrial biopsy performed. If the baseline endometrial biopsy reveals endometrial hyperplasia or cancer or if an office endometrial biopsy cannot be performed the participant will be removed from study. Women with abnormal biopsy results will be referred to contact their Gynecologist from their insurance provider for further treatment for these results.

The study is partially blinded in that investigator and participants will be blinded to the treatment of Metformin versus placebo, but will be un-blinded in regard to the lifestyle intervention. All participants will be followed for at least one month after their last dose of study medication. All treatment-related toxicities will be followed by phone until resolution. All other participants will be randomized to one of four arms:

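### Stopping study drug also ends study participation, and early leavers are scored as zero change, so measurable month-4 Ki-67 values may be replaced by a constant

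*Combined protocol and SAP*

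**What the plan says.** Several rules link stopping treatment to leaving the study:

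- Section 6.4, ALT at 4 times the upper limit of normal or more: "the study drug will be stopped, and participant removed from the study".
- Section 6.4, creatinine at 2.5 times the upper limit or more: the woman "will be taken off of the drug and removed from the study". Reported heart-failure symptoms have the same consequence.
- Section 8.3, heart-failure or renal-failure symptoms: "drug will be stopped and the participant taken off study".
- Section 8.2, suspected non-compliance: "Participants may be removed from the study at the discretion of the investigator". Section 8.5 defines non-compliance as "missing more than 4 consecutive doses per month or a total of more than 10 doses" over the four months.

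Section 9.0 calls the primary analysis intent-to-treat and enters women who discontinue early as having no change from baseline.

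Two passages bear on what happens after removal. Section 5.3.1 schedules the second biopsy about four months "into treatment in all participants from (all four arms) both groups". Section 6.1 states: "All participants will be followed for at least one month after their last dose of study medication", and names only phone follow-up of toxicities. Neither says whether a woman already removed is asked for the month-4 biopsy. The protocol has no status for a woman who is off drug but still on study.

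**The concern.** A woman whose last dose falls in month 1 or 2 can complete the promised month of follow-up before the month-4 biopsy is due. If removal ends her participation, her Ki-67 change is never measured and zero is entered in its place. She stays in her randomised arm, so intent-to-treat is kept in form, but her outcome is assumed.

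The reasons for removal can depend on treatment. Section 8.6 asks for the circumstances of loss to follow-up to be established, "since loss may be related to study drug". Section 3.7 lists asthenia, edema, diarrhea and nausea as metformin side effects. Fatigue and ankle edema are among the heart-failure symptoms that trigger removal in section 6.4, and gastrointestinal effects can lead to missed doses. Section 8.2 refers to study requirements in general. Women in the lifestyle arms have 16 extra sessions to attend, and that assignment is not blinded.

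The factorial design adds a second problem. A woman in a lifestyle arm who meets a drug-safety rule also has her lifestyle response set to zero, although section 1.1.1 aims at the independent effects of both interventions.

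**Working it through.** **Inputs from section 9.0 and section 5.4.** 25 women per arm, SD 0.8, two-sided 5%, 2x2 ANOVA (96 error df). Mean decreases are 0 (control), 3.5 (metformin), 1.75 (lifestyle) and 7 (both).

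**Assumed.** Removal rates of 2% to 20%, removal at random within arm, and the share of the effect still present at month 4 in removed women. The documents give none of these.

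**The plan's own figure.**
- Metformin contrast: (3.5 + 7)/2 - (0 + 1.75)/2 = 4.375.
- Lifestyle contrast: (1.75 + 7)/2 - (0 + 3.5)/2 = 2.625.
- Main-effect SE: 0.8 x sqrt(1/50 + 1/50) = 0.16.
- Interaction contrast: 7 - 3.5 - 1.75 + 0 = 1.75, with SE 0.8 x sqrt(4/25) = 0.32.

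Power is about 100% for both main effects and 99.97% for the interaction, so the stated figure of over 95% reproduces.

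**Dilution, equal removal r in all arms.** Zero coding multiplies every contrast by (1 - r). The SD of an arm with mean m becomes sqrt((1 - r) x 0.64 + r(1 - r) x m^2). At r = 0.20 and m = 7 this is sqrt(0.512 + 7.84) = 2.89. The SD rises above 0.8 only if m exceeds 0.8/sqrt(1 - r), which is 0.89 at 20%. At means of 0.3 and 0.6 it falls, to 0.73 and 0.76.

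Hand check of the interaction at 20%: the contrast is 1.75 x 0.80 = 1.40. The arm variances are 0.512, 2.472, 1.002 and 8.352, which sum to 12.338. The SE is sqrt(12.338/25) = 0.70, the ratio is about 2.0, and power is about one half.

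Simulated interaction power (100,000 trials per entry):

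| Handling of removed women | 2% | 5% | 10% | 20% |
|---|---|---|---|---|
| Set to zero | 0.97 | 0.90 | 0.75 | 0.51 |
| Measured, no effect persists | 0.97 | 0.89 | 0.74 | 0.49 |
| Measured, metformin effect lost, lifestyle effect kept | 0.99 | 0.95 | 0.86 | 0.63 |
| Measured, half the effect persists | 1.00 | 0.99 | 0.98 | 0.92 |

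Main-effect power stays above 0.99 throughout.

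**Smaller effects.** Section 9.0 also mentions effects of 0.3, 0.6 and 1.2. Read as arm means (0/0.6/0.3/1.2), lifestyle power is 0.80 with no removal. At 20% removal it is 0.64 under zero coding. With measured values it is 0.56 if nothing persists, 0.71 if only the lifestyle effect is kept, and 0.69 if half persists. The arm-mean reading matches the plan's 80% for lifestyle but gives the interaction only about 15% power. Read as contrasts, lifestyle power is 46% before any removal.

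**Bias from a shared background change c.** With no drug effect, the false metformin difference has size c x (pM - pP), where pM and pP are the removal rates on metformin and placebo.
- c = 0.25, 10% v 5%: 0.25 x 0.05 = 0.013, type I error 5.1%.
- c = 0.5, 20% v 5%: 0.5 x 0.15 = 0.075, type I error 7.9%.
- c = 1.0, 20% v 5%: 1.0 x 0.15 = 0.15, type I error 15%.

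Measured values give no bias and 5% if removed women share the background change.

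**Bias across factors, zero background.** Take a metformin effect E, no lifestyle effect, and removal of 20% in the lifestyle arms against 5% in the others. The zero-coded lifestyle estimate is E x (0.80 - 0.95)/2.
- E = 3.5: -0.26, significant in about 21% of trials.
- E = 0.6: -0.045, significant in about 6%.

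If the effect fully persists off drug, the whole estimate is false, and measured values give 0 and 5%. If half persists, half is false: measured values give -0.131 for E = 3.5. If none persists, measured values give the same estimate, and it is real.

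**The case against.** The strongest reply is that no loss is demonstrated. Section 5.3.1 schedules the second biopsy for all participants, and the month of follow-up in section 6.1 is a minimum. This stands as a limit on certainty. It does not settle the matter, because a woman removed from the study is not clearly still a participant.

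Second, the mandatory triggers are probably uncommon. Entry criteria exclude raised ALT, raised creatinine and a history of heart failure, and a trigger found at the month-4 visit need not cost the biopsy. Removal of 10% to 20% would need discretionary removals. The 8.5 limit is tight: Table 2 gives 7 + 14 + 21 + 99 x 2 = 240 dosing occasions in 120 days, so 10 missed is 4.2%. But removal on that ground is optional, and investigators are blinded to drug.

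Third, the larger bias figures need strong conditions. The plan assumes zero mean change in controls, and the placebo variability in section 5.3.1 concerns transcripts, not a mean Ki-67 shift. With 10% v 5% removal, type I error from a background change of 1.0 is about 6%, and cross-factor rejection at a metformin effect of 3.5 is about 7%.

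Fourth, measuring may not raise power. With a plasma half-life of about 6.2 hours (section 3.5), little metformin effect may remain months after stopping, although half-life does not determine how long a tissue marker stays changed. If nothing persists, measured values give no gain for the interaction and less lifestyle power in the small-effect case. This also stands. The case for measuring is lower risk of bias.

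Finally, the women concerned may have cardiac, renal or liver signals, and the biopsy is preceded by an NSAID or acetaminophen. A request limited to women for whom it is clinically safe meets this.

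**Conclusion.** The concern holds. The rules end participation along with drug, and the analysis rule then assigns zero change. Primary outcomes that could be measured may therefore be replaced by a constant, for reasons that may differ by arm.

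The size is uncertain. At 2% to 5% removal the effect is modest: interaction power is 0.97 to 0.90 and main-effect tests are untouched. At 10% to 20% the interaction test suffers, at 0.75 to 0.51. Zero coding is also not reliably conservative: with unequal removal and a non-zero change from background or from the other factor, it can produce a false difference. A non-zero background is possible but not shown. The cross-factor case needs no background change, only unequal removal by lifestyle arm and some metformin effect that persists.

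This is a change that should be made, held with medium confidence. It rests on assumed removal rates and persistence, and on the inference that removed women are not biopsied.

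**What to change.** Keep every safety trigger. In sections 6.4 and 8.0, state that a trigger ends study drug and, for heart-failure or renal symptoms or where otherwise clinically indicated, the exercise and lifestyle intervention too. State that neither these events nor non-compliance ends outcome follow-up. Request the scheduled month-4 biopsy and labs where clinically safe and with the woman's agreement. In section 9.0, use observed values in the primary intent-to-treat analysis, keep the zero-change rule only for women with no month-4 biopsy, and report removals by arm and reason.

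The cost is protocol wording, with no procedure beyond the biopsy and labs already scheduled. Some women off drug would be asked for that biopsy. Their values would reflect stopping treatment, so power may not rise and can fall (lifestyle 0.56 against 0.64 in the small-effect case at 20% removal if nothing persists). Voluntary withdrawal and loss to follow-up would remain under the zero-change rule. A missed month-4 biopsy cannot be recovered at analysis, so the change has to be made during conduct.
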